Collaborative-Care Rehabilitation to Improve Functional Outcomes after Dysvascular Amputation

Protocol Version: January 5, 2014

COMIRB Protocol

COLORADO MULTIPLE INSTITUTIONAL REVIEW BOARD
[name] [contact] [contact]

Title: Collaborative-Care Rehabilitation to Improve Functional Outcomes after Dysvascular Amputation

Principal Investigator: [name], PT, Ph.D.
V1.3

SYNOPSIS

Objectives

The objective of this study is to determine the efficacy of a collaborative-care, home-based rehabilitation program for improving functional outcomes following dysvascular transtibial amputation. The primary aim is to determine if the rehabilitation program improves performance-based and participant-report measures of physical function, compared to standard of care, for participants with dysvascular transtibial amputation. The secondary aim is to determine if the rehabilitation program improves daily physical activity, compared to standard of care, for participants with dysvascular transtibial amputation. Two exploratory aims are: 1) determine the efficacy of the intervention for promoting health self-management, measured as participant-reported self-efficacy for managing chronic disease, motivation for exercise, and health-care resource use and 2) identify factors at initial testing that are predictive of physical activity level and disability 24 weeks after intervention.

Design and Outcomes

This will be a randomized, controlled clinical trial on the effects of 12 weeks of collaborative-care, home-based rehabilitation on physical function outcomes. Outcome variables include:

1. Performance-Based Physical Function Measures:
 - a. Timed Up-and-Go (TUG)¹
 - b. Two-Minute Walk (2MW)²
 - c. Five-meter Walk (5mW)³
2. Self-Report Physical Function Measures:
 - a. Prosthesis Evaluation Questionnaire – Mobility Section (PEQ-MS)⁴
 - b. Houghton Scale⁵
 - c. Patient-Specific Functional Scale (PSFS)⁶
3. Activity Measurement:
 - a. Physical activity monitors (Actigraph) worn for 1 week following each test session (baseline, 12-week, 24-week). These monitors are valid tools for measuring relative level of activity (e.g., sedentary, light, moderate, vigorous) for various patient populations⁷⁻⁹ and are valid and reliable spatiotemporal gait measures for patients with lower limb amputation.^{10,11}
4. Self-Efficacy and Motivation:
 - a. Self-Efficacy in Managing Chronic Disease (SEMCD) questionnaire^{12,13}

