The pilot study also examines the comorbidity profile and rehabilitation dose for patients. Data collected to this point have guided development of the proposed intervention (Table 2).

D. Research Design and Methods

Table 2. Standard of care interventions following dysvascular transtibial amputation (n = 14)

Category	Specific Interventions
Gait Training	
 •Level-ground walking •Parallel-bar walking •Community walking •Stair ascent/descent •Treadmill walking
Neuromuscular Re-education	
 • Variable techniques
Therapeutic Exercise	
 •Hip muscle strengthening •Knee muscle strengthening •CV/Endurance training •Hip stretching exercise •Knee stretching exercise •Trunk/Core strengthening
Prosthetic Don & Doff / ADL	
 •Don/doff prosthesis •Basic ADL training
Standing Balance / Pre-Gait Training	
 •Standing weight-shifts •Step-ups •Side-steps •Bilateral standing balance •Single-leg standing balance
Mobility Training	
 •Supine-sit mobility •Sit-stand mobility •Simulated community & home mobility training

Note: Specific categories listed in order of frequency during rehabilitation and specific interventions listed in order of frequency within each category.

initial test session at their home (or the research lab, whichever is more convenient for the participant) and be randomized to group: 1) experimental (EXP) or 2) control (CTL), stratified by sex.

D4. Intervention. Experimental (EXP) Group: Objectives for the collaborative-care, home-

Table 1. Physical function rehabilitation outcomes following dysvascular amputation

	Initial Exam	Discharge
TUG (s)	26.4 (15.3)	12.4 (3.9)
Gait Speed (m/s)	0.57 (0.34)	1.16 (0.33)
TMW (m)	76.8 (22.8)	125.2 (22.4)
PEQ-MS (0-4)	2.4 (1.0)	2.8 (0.7)
PSFS (0-10)	3.5 (2.0)	5.9 (1.1)

Note: TUG: Timed Up-and-Go, TMW: Two-Minute Walk, PEQ-MS: Prosthesis Evaluation Questionnaire – Mobility Section, PSFS: Patient-Specific Functional Scale

N = 14, Rehab Duration = 8.3 (5.8) weeks. All values are mean (SD).

D1. Subjects. Forty-four participants with dysvascular transtibial amputation.

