D2. Inclusion/Exclusion Criteria. Inclusion criteria: 1) DM and/or PAD, 2) unilateral transtibial amputation < 6 months prior to baseline testing, 3) household ambulation using definitive prosthesis prior to baseline testing, 4) participation in physical rehabilitation at time of baseline testing and 5) live within 45 minutes of a participating clinic.

Exclusion criteria: 1) require wheelchair for mobility (use prosthesis only for transfers), 2) ankle-level or above amputation on contralateral limb, 3) traumatic or cancer-related amputation, 4) uncontrolled heart condition, 5) acute systemic infection, 6) pregnancy, 7) decisionally challenged, and 8) prisoners.

Confounding variables will be tracked to allow better delineation of the “dysvascular amputation” population in future studies including: medications, cognitive function (Folstein Mini-Mental State Examination¹⁵), depression (Geriatric Depression Scale SF^{16,17}), residual limb quality (Chakrabarty scoring of residual-limb quality¹⁸), residual limb length, ankle-brachial index of the non-amputated limb, lower extremity sensory testing, pre-amputation ambulatory status (self-report), and type of prosthesis (socket, suspension, and foot). A Comorbidity Assessment tool¹⁶ will be used to document and account for comorbidities.

D3. Screening. Participants will be recruited at the rehabilitation site and screened with a phone call interview. After consent, participants will have an

based rehabilitation program are to: 1) improve physical impairments with targeted exercise, 2) increase physical activity through a home walking program and 3) optimize patient health self-management. The collaborative-care, home-based rehabilitation program was developed based on self-management programs for patients with chronic disease,^{45,46,57}

common physical impairments and functional limitations following dysvascular transtibial amputation,^{36,58-62} published standard of care guidelines based on professional opinion,^{34,63,64} and clinician input from the participating hospital systems (Table 3). Physical impairments and functional limitations will be individually identified at initial testing and interventions chosen with collaboration of participant and researcher. Participants will be contacted once/week via phone to discuss progress toward individual intervention goals. Barriers to achieving goals will be discussed and new goals created on a weekly basis during the phone or home visits.

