The exercise program will be tailored to each participant and includes targeted exercise to strengthen trunk, hip, knee, and ankle musculature (Table 3). Weakness in these muscle groups is identified in the literature^{36,65} and by collaborating clinicians for this study. Therapists treating the participant prior to enrollment will help prioritize the targeted muscle groups for each participant, based

* List of options for strengthening program, priority muscles to be included in the program based on patient-researcher collaboration, with input from primary PT.

on participant-specific muscle weakness identified during rehabilitation. The participant (along with researcher collaboration) will then identify specific exercises from a menu of progressive exercises to target each muscle. Exercises will be performed at home independently by the participant, assessed weekly and advanced through participant-researcher interaction, with the goal of performing strengthening exercises 3 days/week for 20 minutes/session.

Other exercises target hip and knee joint contracture prevention, two common joint mobility problems for patients with transtibial amputation.⁶³ Presence of contractures of the hip and/or knee are predictors of poor physical rehabilitation outcome.³⁵ Included are static stretches (e.g., prone lying and seated with knee propped into extension) performed 2-3 X/week for 2 minutes each (total 4 minutes).

The walking program will be performed all 12 weeks, with the goal of walking at least 3X/week. Initial walk duration will be determined at the first visit and goals set weekly by the participant with a guideline of at least 5 minutes of increased walking weekly. Once 30 minute duration is achieved, intensity will be progressed based on targeted heart rate or other health-specific parameters such as claudication intensity. Similar programs have improved symptoms, walking distance, and quality of life for people with PAD.^{45,46}

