
D7 Outcome Measures. Participants will have three test sessions of 1.5 hours each (initial, 12-week (primary end-point), 24-week) beginning within three weeks of completing outpatient rehabilitation. All sessions will occur at the participant's home or Interdisciplinary Movement Science Lab (IMSL), whichever is more convenient for the participant, using standardized protocols by research assistants.

- **Physical Function Outcomes:** Three physical performance tests will be used: the Timed Up-and-Go (TUG)¹, 2-Minute Walk (2MW)², 5-meter Walk (5mW)³, and Single-Limb Stance tests. Self-report measures of physical function include the Prosthesis Evaluation Questionnaire – Mobility Section (PEQ-MS)^{4,71}, Houghton Scale⁵, Patient-Specific Functional Scale (PSFS)⁶, and the World Health Organization Disability Assessment Schedule 2.0. Each of these are reliable and valid measures for people with chronic disease.^{4,62,69,72-76}
- **Activity Measurement:** Physical activity will be assessed with physical activity monitors (Actigraph) worn for 1 week following each test session. These monitors are valid tools for measuring relative level of activity (e.g., sedentary, light, moderate, vigorous) for various patient populations⁷⁻⁹ and are valid and reliable spatiotemporal gait measures for patients with lower limb amputation.^{11,77}
- **Self-Efficacy and Motivation:** Self-efficacy and exercise motivation will be used as descriptive measures related to health self-management. The Self-Efficacy in Managing Chronic Disease (SEMCD) questionnaire has been used as an outcome for self-management of various chronic diseases.^{12,13} The Intrinsic Motivation Inventory (IMI) Interest and Enjoyment Subscale measures participant-reported interest and enjoyment related to the intervention.¹⁴ Participant compliance with daily health monitoring will be tracked as number of days missed/possible days.

Procedural reliability is critical to the success of the proposed and future studies with multiple clinical sites. The PI will oversee standardization and implementation of testing and intervention. The PI will provide 2-3 training sessions, including a training manual, for each designated tester. If procedural reliability is below 0.90, additional training sessions will be scheduled.

E. Study Timeline and Enrollment Goals

Task	Year 1			Total	Year 2				Total	Year 3			Total
Training of Personnel													
Screening & Enrollment	3	3	4	n=10	5	5	5	5	n=30	5	5	4	n=44

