Collaborative-Care Rehabilitation to Improve Functional Outcomes after Dysvascular Amputation

Statistical Analysis Plan
Version Date: 01.05.2014

Between-group differences in all outcomes at 12- and 24-week tests will be evaluated using maximum likelihood estimation in a multivariate repeated measures model. The maximum likelihood method uses all available data and provides unbiased estimates under the assumption that missing data are missing at random. The model for each outcome will be controlled for baseline value of the outcome, rehabilitation clinic site (VA/non-VA), diagnosis of DM, and diagnosis of PAD. Estimated group means and within-group mean changes over time for each outcome will be reported with 95% confidence intervals. This early phase study is powered for one endpoint; multiple secondary endpoints are reported to guide further research without adjustment for multiplicity.

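### The plan does not keep the baseline activity week ahead of randomisation, so the value used to adjust the Secondary Aim may be post-allocation and may shrink its estimate

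*Protocol*

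**What the plan says.** - **When activity is recorded.** D7 (Activity Measurement): "Physical activity will be assessed with physical activity monitors (Actigraph) worn for 1 week following each test session". The outcome list in the Synopsis names the sessions: "worn for 1 week following each test session (baseline, 12-week, 24-week". The baseline week therefore comes after the baseline session.
- **When participants are randomised.** D3, in a sentence interrupted by the table layout: "After consent, participants will have an" ... "initial test session at their home (or the research lab, whichever is more convenient for the participant) and be randomized to group".
- **How the intervention is planned.** D4: "Physical impairments and functional limitations will be individually identified at initial testing and interventions chosen with collaboration of participant and researcher". On walking: "The walking program will be performed all 12 weeks, with the goal of walking at least 3X/week", and "Initial walk duration will be determined at the first visit". D4 also gives experimental participants pedometers and an exercise diary.
- **How baseline is used.** SAP: "The model for each outcome will be controlled for baseline value of the outcome". Protocol D5 analyses activity level at 12 weeks by the method used for Timed Up-and-Go (TUG), which includes the baseline value. Its longitudinal model also conditions on baseline.
- **What depends on it.** Physical activity is the only outcome of Specific Aim 2, with hypotheses at 12 and 24 weeks.

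**The concern.** A baseline covariate should be fixed before allocation can influence it. Session-based measures such as TUG meet that condition, because D3 puts testing before randomisation. Activity is different: its baseline takes a further week to collect, and D3 and D7 do not say whether randomisation waits for that week.

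If it does not wait, an experimental participant could spend the baseline week knowing the assignment, with walking goals and a pedometer. Adjustment would then remove part of the effect that the Secondary Aim is meant to estimate. The protocol intends its results to indicate how large the effect is for planning later research, so an understated estimate would carry forward. The SAP's maximum likelihood method deals with outcomes missing at random. It does not repair a covariate that treatment has moved.

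**Working it through.** **The plan's own figure.** No power or sample size is given for activity. The only calculation (D6) is for TUG: difference 6.0 s, SD 6.0, so d = 6.0/6.0 = 1.0, with 17 per group for 80% power. A two-sided t test at 0.05 (sidedness is not stated, so two-sided is assumed) gives 80.7% power at 17 per group and 78.1% at 16. The figure reproduces, and the present point does not touch it.

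**Formula.** Let B be true pre-treatment activity, g the group (0 or 1), τ the 12-week effect and b the within-group slope of 12-week activity on baseline:

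Y = a + b·B + τ·g + error

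If a share f of the effect is already present in the monitor week, the recorded baseline is B* = B + f·τ·g. Substituting B = B* − f·τ·g:

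Y = a + b·B* + τ(1 − b·f)·g + error

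The adjusted estimate therefore targets τ(1 − b·f), and the understatement is b·f. At 24 weeks the same early difference is subtracted, multiplied by the slope for that visit.

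**Inputs.** The documents give neither b nor f. Both are assumptions, shown as ranges. If the effect builds evenly over the 12 weeks, week 1 carries f = 1/12.

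| f (assumed) | b = 0.5 | b = 0.7 | b = 0.8 |
|---|---|---|---|
| 0 (disclosure and intervention held) | 0% | 0% | 0% |
| 1/12 | 4.2% | 5.8% | 6.7% |
| 0.10 | 5% | 7% | 8% |
| 0.25 | 12.5% | 17.5% | 20% |
| 0.50 | 25% | 35% | 40% |

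**Simulation check** (17 per group, 10,000 runs, τ = 1.0 SD, b = 0.7, equal SDs). Mean adjusted estimates were 1.003, 0.824 and 0.649 for f = 0, 0.25 and 0.50. The formula gives 1.00, 0.825 and 0.65.

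**Illustrative power** (17 per group, b = 0.7, two-sided 0.05, noncentral t with 31 df, SE = √(1 − b²)·√(2/17 + (fτ)²/30)). For τ = 1.0 and f = 0.25, SE = 0.714 × √(0.1176 + 0.0021) = 0.247 and 0.825/0.247 = 3.34, giving 89.9%.

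| f | τ = 1.0 SD | τ = 0.5 SD |
|---|---|---|
| 0 | 97.7% | 50.7% |
| 0.10 | 95.7% | 45.2% |
| 0.25 | 89.9% | 37.0% |
| 0.50 | 70.0% | 24.7% |

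The effect sizes here are also assumptions.

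**The case against.** The strongest reply is that the schedule is unstated rather than wrong. D3 gives an order, test and then randomise, but no day for randomisation, disclosure or first intervention contact. In D4, the reference to initial testing belongs to identifying impairments, not necessarily to choosing interventions. The first visit, at which walk duration is set, may be a later and separate visit. Figure 2, which D4 cites for the contact schedule, is not reproduced in the text available and may bear on this. All of that stands. A reader might infer that participants are definitely randomised and started on the programme at the baseline session; the documents do not establish it. Nor do they put the monitor week before allocation.

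The reply also holds on size. D4 describes a walking programme that builds week by week, so a first-week share of 25–50% is a high assumption. An even build-up gives about 4–7%. An early response to pedometers could raise it, but the documents do not settle this.

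Two further inferences are tempting and not supported:

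- **Loss of the full share f.** That would apply to an unadjusted change score. The planned between-group comparison is baseline-adjusted, so the loss is b·f.
- **Weaker prediction in Exploratory Aim 2.** That aim predicts 24-week outcomes regardless of group. A first-week value that includes a lasting early response could predict 24-week activity better, not worse.

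Finally, activity is a secondary outcome, and the SAP says the study is powered for one endpoint. That limits the consequence but does not remove it, because Specific Aim 2 rests entirely on activity.

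**Conclusion.** The point holds in conditional form. As written, the schedule permits a post-allocation baseline for activity, and both documents adjust for that value. If allocation is known or intervention begins during the monitor week, the Secondary Aim estimate is multiplied by (1 − b·f). With b of 0.5–0.8, that is an understatement of about 4–7% for an even build-up, 5–8% at f = 0.10, 12.5–20% at f = 0.25 and 25–40% at f = 0.50. If disclosure and intervention are in practice held until the week ends, there is none.

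The direction toward zero assumes a positive baseline slope and a first-week group difference of the same sign as the 12-week effect. Both are plausible, since the walking programme and pedometers act directly on activity. The point is confined to the activity-monitor outcome. TUG, the other session-based measures and the powered primary analysis are unaffected, and no claim is made about Exploratory Aim 2.

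**What to change.** In D3 and D7, state the order: baseline tests; one week of monitor wear, completed; then randomisation. If randomisation cannot wait, then at minimum hold disclosure of allocation, issue of pedometers and goal setting until that week is complete. If this is already the practice, one sentence suffices.

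The cost is about one week's delay per participant. The amputation-to-enrolment limit in D2 is counted to baseline testing, so the delay would not make anyone ineligible on that criterion. A few people may be lost before randomisation. This does not bias the comparison, but it matters slightly for recruitment: D6 projects 150 × 0.60 × 0.50 = 45 consenting patients for a target of 44, a margin of one.

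The 12- and 24-week visits need not be re-based to randomisation.

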 - b. Intrinsic Motivation Inventory (IMI) Interest and Enjoyment Subscales¹⁴
 - c. Participant compliance with exercise will be tracked as number of exercise sessions missed/possible sessions.
5. Healthcare Use:

- a. Number of healthcare provider visits scheduled and attended; from electronic medical record.
- b. Number of hospital contacts (emergency department visits and hospital admissions); from electronic medical record.

Interventions and Duration

Forty-four participants will be randomly assigned to two groups: 1) experimental (EXP) or 2) control (CTL). The entire intervention period is 12 weeks, with the primary end point at 12 weeks. At 24 weeks after initiation of intervention, each group will be asked to return for a follow-up test session.

Evaluations will take place using the following schedule:

Baseline, 12 and 24 weeks: Physical Performance Tests, Self-Report Physical Function Measures, Activity Measurement, Self-Efficacy questionnaire, Motivation questionnaire, Health Status questionnaire, and healthcare use assessment.

Baseline only: At Baseline testing, participants will also complete the following tests/measures/forms: 1) Folstein Mini-Mental State Examination,¹⁵ 2) Geriatric Depression Scale SF,^{16,17} 3) Chakrabarty scoring of residual-limb quality,¹⁸ 4) Residual limb length, 5) lower extremity sensory testing, 6) pre-amputation ambulatory status report, 7) type of prosthesis (socket, suspension, and foot), and 8) demographic information. Hemoglobin A1c measurements (for DM) and confirmation of PAD will be extracted from the participant medical records.

Continuously: Falls, Adverse Events (AEs), and Serious Adverse Events (SAEs) will be recorded and reported as needed.

Sample Size and Population

The target sample is 44 persons with recent transtibial amputation, resulting from PAD or DM complications.

Participants will be recruited from the University of Colorado Hospital and Denver Health.

Title: Collaborative-care rehabilitation to improve functional outcomes after dysvascular amputation

A. Abstract & Specific Aims

The primary objective of this project is to determine the efficacy of a collaborative-care, home-based exercise program for improving physical function, activity level, and health self-management within the first year following dysvascular transtibial amputation.

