Results of this study will quantify the effect size of the proposed intervention and inform future research designed to optimize intervention, focus examination based on the dominant pathophysiology (i.e., DM, PAD, or both), and examine efficacy in other populations (e.g., patients with trans-femoral amputation).

Specific Aim 1: The Primary Aim (PA1), on which this trial is powered, and the Primary Hypotheses (H1.1 and H1.2) are:

- a) PA1: Determine if the collaborative-care, home-based rehabilitation program improves performance-based and participant-report measures of physical function compared to standard of care for participants with dysvascular transtibial amputation.

[figure not shown]

Figure 1. Outcome factors after amputation

- b) H1.1: The rehabilitation program will result in greater improvements in the performance-based measures of the Timed Up-and-Go, 2-Minute Walk, and 5-meter Walk tests than standard of care at 12 weeks (primary end-point) and persist at 24 weeks following initiation of intervention.
- c) H1.2: The rehabilitation program will result in higher ratings of participant-reported physical function on the Prosthesis Evaluation Questionnaire – Mobility Section, Houghton Scale, and Patient-Specific Functional Scale than standard of care at 12 weeks (primary end-point) and persist at 24 weeks following initiation of intervention.

Specific Aim 2: The Secondary Aim (SA) and Hypothesis (H2) are:

- a) SA: Determine if the collaborative-care, home-based rehabilitation program improves physical activity when compared to standard of care for participants with dysvascular transtibial amputation.
- b) H2: The rehabilitation program will result in greater increases in physical activity than standard of care at 12 weeks (primary end-point) and persist at 24 weeks following initiation of intervention.

Exploratory Aims:

1. Exploratory Aim 1 (EA1) and Hypotheses (H3 & H4) are:

- a) EA1: Determine if the collaborative-care, home-based rehabilitation program influences the health self-management factors of self-efficacy for managing chronic disease, motivation for exercise, and healthcare use.
- b) While the study will likely be under-powered to find differences related to this aim, the, if trends in group differences are seen, data will provide a means for performing a statistical power analysis to determine sample size for future study. The hypothesized trends for group differences are:

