 - (1) H3: The rehabilitation program group will tend to have greater positive change in ratings on the Self-Efficacy in Managing Chronic Disease (SEMCD) questionnaire and Intrinsic Motivation Inventory (IMI) Interest and Enjoyment Subscales, compared to the standard of care group at 12 and 24 weeks following initiation of intervention.
 - (2) H4: The rehabilitation program group will tend to have higher numbers of attended healthcare provider appointments and lower numbers of hospital contacts at 12 weeks and 24 weeks, compared to the standard of care group.

2. Exploratory Aim 2 (EA2) and Hypothesis (H4) are:

- a) EA2: Identify factors predictive of physical activity level and disability measured by activity monitors and self-reported disability (World Health Organization Disability Assessment Schedule 2.0), respectively.
- b) H5: Significant predictors of physical activity and disability will be identified from the categories of demographic/anthropometric, activity/mobility, health behaviors, physical health, amputated-limb health, contralateral-limb health, cognitive/affective health, and healthcare use factors for participants at 24 weeks following intervention, regardless of group assignment.

B. Background and Significance

B1. Significance. Limitations in physical function are common following dysvascular major lower limb amputation.^{28,29,31} This is a significant issue considering that dysvascular amputation is becoming increasingly more common in the United States. Dysvascular amputation is operationally defined as amputation resulting from severe PAD with critical limb ischemia or severe DM with dense distal sensory and motor neuropathy leading to a non-healing wound (or a combination of these two related, but separate pathophysiologies). The projection of 2.3 million people living with amputation in the United States by the year 2050 represents an increase of nearly 100% from current values.¹⁹ As a result, dysvascular amputation has become a major healthcare issue in the U.S, including an economic problem.³²

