Health self-management will be promoted in 3 primary ways: 1) action plan development with participant-directed goal setting, 2) participant self-tracking of activity (pedometers and exercise diary), and 3) participant education on problem-solving skills to manage chronic health conditions. Participants will also monitor their individual health condition (e.g., heart rate, time to claudication with walking, blood sugar, and blood pressure). These data will focus the weekly discussions (home or phone) over the 12-weeks.^{44,66,67}

Control (CTL) Group: CTL group participants will be contacted at the same interval (phone and home visits) as the EXP group (Figure 2) to ensure attention control between groups. Visits will

Table 3. EXP Group Rehabilitation Program

Category	Specific Components
Impairment-Based Exercise	
A. Strengthening* (3x/week)
 
Hip Extensors Hip Abductors Hip Adductors Knee Extensors Knee Flexors Ankle Plantar Flexors (intact limb) Trunk Stabilization
 
B. Stretching (3x/week)
 
Hip Flexors Knee Flexors

Activity-Based Intervention	• Walking Program (3x/week)
Health Self-Management	
 • Participant-tailored goals • Participant self-tracking of exercise and activity • Participant education on problem-solving skills for managing health

* List of options for strengthening program, priority muscles to be included in the program based on patient-researcher collaboration, with input from primary PT.

consist of recording problems reported by the participant. If health or rehabilitation questions arise that require professional advice during participant-researcher visits, the participant will be referred to his/her healthcare provider.

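### D7 ties the IMI to the intervention, so as worded the IMI contrast in H3 would compare ratings of different things, not motivation for exercise

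*Protocol*

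**What the plan says.** Exploratory Aim 1 (Abstract & Specific Aims) asks whether the programme influences the "health self-management factors of self-efficacy for managing chronic disease, motivation for exercise, and healthcare use". H3 opens "The rehabilitation program group will tend to have greater positive change in ratings on the Self-Efficacy" and goes on to name two instruments, the self-efficacy questionnaire (SEMCD) and the IMI Interest and Enjoyment Subscales. Both are compared with standard of care at 12 and 24 weeks.

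D7, under Self-Efficacy and Motivation, gives two descriptions in one bullet. It begins: "Self-efficacy and exercise motivation will be used as descriptive measures related to health self-management". It then says of the IMI: "Interest and Enjoyment Subscale measures participant-reported interest and enjoyment related to the intervention".

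The Synopsis schedules the motivation questionnaire at baseline, 12 and 24 weeks. D3 places the initial test session before randomisation. D4 says that control visits "consist of recording problems reported by the participant".

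The SAP states: "Between-group differences in all outcomes at 12- and 24-week tests will be evaluated using maximum likelihood estimation". It adjusts each outcome for its own baseline value and also reports within-group mean changes.

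Compliance appears in the same outcome group. The Synopsis says: "Participant compliance with exercise will be tracked as number of exercise sessions missed/possible sessions". D7 instead counts missed days of health monitoring over possible days.

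**The concern.** A between-arm comparison of a rating scale needs both arms to be rating the same thing, and a change score needs the same thing to be rated at both times. If the IMI items ask about the intervention, neither condition is met. A higher score in the experimental arm could mean only that people enjoy an exercise programme more than a contact in which their problems are written down. That can happen with no difference between arms in how motivated anyone is to exercise.

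What is at stake is the stated use of this aim. The protocol accepts that it is likely to be under-powered and wants the data for sizing a later study. Low power makes an effect estimate imprecise. A mismatched referent makes it an estimate of something else, and a larger sample does not correct that.

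**Working it through.** No figure in the documents depends on this point, so the check is mainly a comparison of texts.

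**1. What the IMI would rate under each wording**

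| Visit and arm | D7, IMI sentence (the intervention) | Aim 1 and opening of the D7 bullet (exercise) |
|---|---|---|
| Baseline, both arms | No trial intervention yet: testing precedes randomisation (D3) | Exercise |
| 12 and 24 weeks, experimental | Exercise, walking and self-management programme (D4, Table 3) | Exercise |
| 12 and 24 weeks, control | Phone and home contacts that record problems (D4) | Exercise |

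At baseline a respondent asked about the intervention might rate usual rehabilitation, since D2 requires participation in it at that time. That would be a third object.

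**2. What the contrast would estimate under the D7 wording**

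Let E be the mean rating of the programme, C the mean rating of the control contacts, and R_E and R_C the mean baseline ratings of whatever respondents had in mind.

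- Contrast of changes = (E − R_E) − (C − R_C).
- Randomisation makes R_E and R_C equal in expectation, so the contrast reduces to E − C: liking of the programme minus liking of the contacts.
- The missing baseline object does not by itself bias the between-arm contrast. It does leave the within-group changes (E − R_E and C − R_C) without a meaning, and it leaves the baseline covariate measuring something other than the follow-up score.
- The main fault is that E and C are ratings of different objects.

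**3. How much of H3 is affected**

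The SEMCD concerns managing chronic disease. It makes no reference to the intervention and can be asked alike in both arms and before treatment. Only the IMI half of H3 is affected: two between-arm contrasts (12 and 24 weeks) and four within-group changes (2 arms × 2 follow-up visits).

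**4. Power, for context only**

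The sole design calculation is for the Timed Up-and-Go (D6): difference 6.0 s, SD 6.0, 80% power, 17 per group. D5 gives alpha 0.05; I assume it is two-sided.

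- Normal approximation: n = 2 × (1.960 + 0.842)² × (6.0/6.0)² = 15.7, so 16 per group.
- Two-sample t-test: n = 16.7, so 17 per group, with power 80.7%. The stated figure reproduces.
- With 17 per group, the effect detectable with 80% power is about 0.99 SD. The documents give no IMI effect size. Over an assumed range of 0.3, 0.5 and 0.8 SD, power is about 14%, 29% and 62%.

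This agrees with the protocol's own statement about power. It is a separate limitation from the referent problem.

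**5. Compliance**

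The Synopsis lists it under outcome variables, which on its face brings it within the SAP's wording. It is not among the measures scheduled for the test sessions, not in D5's list of secondary analyses, and not in H3. Assigned exercise and self-monitoring are described only for the experimental arm, and neither definition names an arm.

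**The case against.** The strongest reply is that the IMI referent is not fixed as the intervention. The Synopsis, Exploratory Aim 1 and the opening of the D7 bullet all speak of motivation for exercise. Only one clause says otherwise, and the questionnaire stem is not in the documents. If the items in use ask about exercise, they have much the same meaning in both arms and at baseline, when participants are in rehabilitation or have recently completed it, and the problem largely disappears. That stands: the documents show a contradiction, not a proven fault in the instrument. But the other phrases name the construct. The D7 clause is the only sentence that says what the items refer to, and staff following it would collect scores that are not comparable.

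The second reply is that little hangs on it. The aim is exploratory, D7 calls these measures descriptive, and D5's secondary list omits the IMI. This also stands and limits the weight of the point. It does not remove it, because H3 is directional and the SAP models all outcomes between groups.

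Two stronger readings are tempting and should be resisted:

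- A reader might infer that H3 as a whole cannot be answered. The documents do not support that, since the SEMCD half is unaffected and compliance is not part of H3.
- A reader might infer that the plan includes a compliance comparison that is undefined for the whole control arm (22 of 44 under equal allocation). The zero denominator is inferred from the arm descriptions. No passage specifically plans that comparison; only the breadth of the SAP's wording takes it in.

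**Conclusion.** The point holds in a limited form. If D7 is followed as written, the baseline-adjusted IMI contrast at 12 and 24 weeks compares enjoyment of two different things, and the changes from baseline have no trial object at their starting point. Neither would measure change in motivation for exercise, and an IMI effect size taken forward to a later study would be for the wrong construct.

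This rests on the items being worded as D7's IMI sentence describes, which the documents do not let one confirm. No size of bias can be given. The primary analysis, the sample size, Aims 1 and 2 and the SEMCD part of H3 do not change. The correction is still worth making because it is nearly free, protects the stated purpose of the aim, and cannot be made once baseline questionnaires have been collected. The compliance discrepancy is a minor matter of reconciliation.

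**What to change.** In D7, state one referent for the IMI items that applies in both arms and at all three visits, such as exercise and walking, in line with Exploratory Aim 1. Use the same questionnaire stem throughout. If enjoyment of the programme itself is also wanted, keep it as a separate item for the experimental arm at 12 weeks and report it descriptively, with no between-arm test.

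As a tidy-up, reconcile the Synopsis and D7 definitions of compliance. Add one sentence to the SAP saying that compliance is reported descriptively in the experimental arm and is not part of the model for all outcomes.

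The cost is one change to the questionnaire stem, one reconciled definition and one SAP sentence, with no added visits or participants. The downside is that the IMI score no longer describes enjoyment of the programme unless the separate item is kept.
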